4. STUDY INFORMATION

Location(s) of Research Activity: Loma Linda University Medical Center

Expected Start/Stop Dates of Research: 07/01/2021 to 06/30/2023

Special Time Sensitivities: N/A

Type of Research: Randomized controlled trial of two alternative standard-of-care transfusion strategies

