6. SUBJECT RECRUITMENT & SCREENING

Based on the results from Cotton et al, median transfusion in the component therapy group was 6 PRBC in the first 24 hours and 4 PRBC equivalents in the whole blood group. The standard deviation (estimated from the interquartile range) was approximately 4. Thus with an expectation of alpha = 0.05 and expected power of 90% to detect a similar 2 unit difference in transfusion volume, a sample size of 190 should be sufficient; thus our projected sample size of 200 should be more than adequate. Age range will be 18 years and older, and only males will be included in the study. Our expected racial/ethnic distribution will be approximately 60% white, 15% black, 8% Asian, and 18% other race. No actual recruitment will be performed; rather all qualifying patients will be included. Consent waiver is being requested.

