 - 4. Percentage of patients with maximum thrombolysis > 15%
- 6. Interval analyses to be performed after 6 and 12 months with provision to continue the study out to 24 months.
 - 1. Stopping rule: A statistically significant difference in hospital mortality at 6 months or 12 months
 - 1. If in favor of LTOWB, consideration of trial termination and making LTOWB the primary standard of care for all trauma patients receiving emergency transfusion except for child-bearing age females (unless Rh immunoglobulin can be administered)
 - 2. If in favor of component therapy, consideration of trial termination and making component therapy the primary standard care for all trauma patients receiving emergency transfusion
- c. Procedures involved (Research Interventions)

*Chronological order of all research interventions, **distinguishing standard of care vs. research intervention.***

- 1. Level A trauma paged out with gender of patient
- 2. For female patients, care proceeds as normal
 - 1. Standard trauma cooler containing 4 units O- PRBC and 4 units FFP dispatched to trauma bay (if overall supply is short the first cooler may contain 2 units O- PRBC and 2 units FFP)
 - 2. Transfusion proceeds per trauma and ED team
 - 3. Patient data not included in the study

3. For male patients, the blood bank will randomize patients to the LTOWB group or the CT (component therapy) group based on a prespecified calendar-based randomization scheme by week:
 1. LTOWB: Cooler containing 2 or 4 units of LTOWB dispatched to trauma bay depending on supply
 2. CT: Standard trauma cooler containing 4 units O+ PRBC and 4 units FFP dispatched to trauma bay (if overall supply is short the first cooler may contain 2 units O+ PRBC and 2 units FFP)
 3. Transfusion proceeds per trauma and ED team
 4. Blood work (CBC, BMP, tox screen, ROTEM viscoelastic test, PT/INR, PTT, venous lactate) sent as per standard of care for all patients.
 5. Hemorrhage control and other diagnostic evaluations performed in all patients per standard of care.
 6. Patients arrive in ICU and have additional blood work (CBC, CMP, possibly ABG, ROTEM viscoelastic test, PT/INR, PTT, venous lactate, possibly fibrinogen) sent per standard of care by the ICU team.
 7. Clinical data on survival and transfusion monitored
- d. Alternative procedures, if any, that are not included in the study but might be advantageous to the subject. N/A

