11. DATA ANALYSIS

Analysis to be performed by median/IQR with nonparametric comparison of medians for central tendency. P value of 0.05 indicates statistical significance. Patients with death on arrival will be excluded from data reporting as they are a different patient population. Intentional sub-analysis will be performed on patients who received less than 6 units PRBC or equivalent in the first 4 hours or 6 units and more PRBC in the first 4 hours (massive transfusion). Also, an intentional sub-analysis will be performed on the patients who were classified as dead on arrival. Separate sub-analyses will be performed on patients with Abbreviated Injury Score (Head) of 3 or greater indicating severe traumatic brain injury.

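### Arms are assigned by calendar week, but the primary comparison, the mortality stopping rule and the planned database take no account of week

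*Combined protocol and SAP*

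**What the plan says.** All references are to the combined protocol and SAP.

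- **Assignment.** In Section 8.c, step 3, the blood bank allocates men "based on a prespecified calendar-based randomization scheme by week". The text speaks of randomising patients but describes no patient-level step. It does not say whether the weeks are in random order, blocked or alternating.
- **Primary analysis.** Section 11: "Analysis to be performed by median/IQR with nonparametric comparison of medians for central tendency", and "P value of 0.05 indicates statistical significance". No test is named and there is no term for week.
- **Stopping rule.** Section 8.b, item 6: "Stopping rule: A statistically significant difference in hospital mortality at 6 months or 12 months". The consequence is worded as "If in favor of LTOWB, consideration of trial termination", with a parallel clause for component therapy. Again no test is named and week is not mentioned.
- **Sample size.** Section 6 uses a 2-unit difference, SD 4, alpha 0.05 and 90% power: "a sample size of 190 should be sufficient; thus our projected sample size of 200 should be more than adequate". It gives no ICC and no number of weeks.
- **Data.** Section 9 lists the treatment group but no arrival date, week or block. The master list links study ID, MRN and arm (Section 10). Section 15 provides for it, with the assignment list, only while data are being collected, and says that the database will hold no PHI.
- **Duration.** Section 4: "Expected Start/Stop Dates of Research: 07/01/2021 to 06/30/2023".

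**The concern.** The week is the unit of assignment, whereas the planned comparisons treat the man as the unit. If men who arrive in the same week have correlated outcomes, and the weeks were put in random order, the difference between arms varies more than a patient-level test assumes, and its p-values are then too small.

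The documents show one factor that men in the same week might share. Section 8.c says "Cooler containing 2 or 4 units of LTOWB dispatched to trauma bay depending on supply", with a similar short-supply clause for component therapy, and the primary outcome is units transfused.

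At stake are the nominal level of the primary test and, to a lesser degree, of the mortality looks, which carry the only stated stopping criterion. The planned fields would also not allow anyone to check whether week matters.

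**Working it through.** **1. The plan's own figure.** With difference 2, SD 4, two-sided alpha 0.05 (sidedness assumed) and 90% power, n per arm = 2 × (1.960 + 1.282)² × 4² / 2² = 84.1, rounded up to 85, or 170 in total. A t test needs 172. A rank test with efficiency 0.955 needs 85 / 0.955, rounded up to 90 per arm, or 180. The stated 190 does not follow from the stated inputs; it would follow from an unstated 10% loss (85 / 0.90, rounded up to 95 per arm). Here this matters only because it shows that 200 has some slack.

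**2. Weeks and men per week.** The Section 4 dates span 730 days, and 730 / 7 = 104.3 weeks. 200 / 104.3 = 1.92 men per week. If all 200 accrued in half that time, it would be 3.84 per week.

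**3. Primary test ignoring week, random week order.** With Poisson weekly counts of mean m, the design effect is DE = 1 + m × ICC. The type I error of an unadjusted test is about 2 × [1 − Φ(1.96 / √DE)]. At ICC 0.05: DE = 1 + 1.92 × 0.05 = 1.096, 1.96 / 1.047 = 1.872, error 6.1%. The simulated columns use a Mann-Whitney test, equal weeks per arm and normal week effects (10,000 trials per cell, Monte Carlo SE about 0.2 points). Every ICC is an assumption.

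| ICC | DE, 104 weeks | Formula | Simulated, 104 weeks | Simulated, 200 men in 52 weeks |
|---|---|---|---|---|
| 0 | 1.00 | 5.0% | 4.5% | 5.0% |
| 0.02 | 1.04 | 5.4% | 5.1% | 5.9% |
| 0.05 | 1.10 | 6.1% | 5.9% | 7.1% |
| 0.10 | 1.19 | 7.3% | 6.7% | 9.0% |

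A literal median test gives 3.5 to 4.5% over this ICC range (104 weeks), but has only about 75% power for the planned effect. Mann-Whitney is therefore the more natural reading of Section 11.

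**4. If weeks strictly alternate.** With smooth seasonal drift, the unadjusted Mann-Whitney test shows no inflation: 4.6, 5.0 and 5.1% at ICC 0.05, 0.10 and 0.20. A week-clustered rank test is conservative there: 4.0, 3.5 and 2.6%.

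**5. Mortality looks ignoring week.** Assumptions: 25% deaths, 1.92 men per week, random week order.

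| Test and look | ICC 0 | 0.05 | 0.10 |
|---|---|---|---|
| Pooled z, 26 weeks | 5.2% | 5.9% | 7.5% |
| Pooled z, 52 weeks | 5.4% | 6.3% | 6.8% |
| Fisher, 26 weeks | 3.2% | 3.9% | 4.9% |
| Fisher, 52 weeks | 4.0% | 4.7% | 5.2% |

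With pooled z at 0.05, the chance of a false signal at either look is 8.3% at ICC 0, 10.5% at 0.05 and 12.2% at 0.10. Repeated testing alone takes it from 5% to 8.3%.

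**6. Power at 200 analysed men, 104 weeks.** By the normal formula, the 90% point is at ICC = (200 / 170 − 1) / 1.92 = 0.092. With rank efficiency 0.955 it is about 0.064. Simulating a week-clustered rank test gives 92.0, 89.8 and 87.6% at ICC 0, 0.05 and 0.10. So 90% holds up to an ICC of roughly 0.05 to 0.09.

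**7. Do week-aware tests hold their level?** Over ICC 0 to 0.20 in random week order, the clustered rank test runs at 4.7 to 5.6%; separate, smaller runs ranged from 4.6 to 6.2%. For mortality, week-level re-randomisation runs at 4.3 to 4.7% at 26 weeks (about 22 weeks with any patient) and 4.6 to 5.1% at 52. Ordinary clustered standard errors at 26 weeks give 5.9 to 6.5% on t and 8.2 to 8.9% on z, so a small-sample method is needed.

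**The case against.** The strongest reply is that the harm is conditional and small. It needs variation between weeks that the documents neither state nor quantify. At 1.9 men per week the primary error is 5.1% at ICC 0.02 and 5.9% at 0.05. The supply clause is a thin mechanism: it does not say that supply varies by week, later transfusion is left to the clinical team, and the clause does not explain clustered deaths. The scheme is prespecified and the lists exist during data collection, so week can be recovered at both interim looks. A clustered test may also be the wrong primary test if the weeks alternate.

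Most of this stands, and it sets the size of the point. It does not remove it. No step to recover week is planned, the route to it is provided for only while data are being collected, and without week nobody can show that the effect was negligible.

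Three stronger readings are tempting, and the documents support none of them:

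- **That the error is two or three times nominal.** Simulated errors of 9.7% (104 weeks) and 13.5% (52 weeks) need an ICC of 0.20, which nothing in the documents suggests; the second also needs all 200 men in half the planned period.
- **That week is the main fault of the stopping rule.** The inflation largely disappears with Fisher's test, and most of the false-signal risk comes from repeated looks at 0.05. A significant result also prompts consideration of stopping, not automatic stopping.
- **That the trial is underpowered because of clustering.** The slack between about 170 to 180 and 200 absorbs small ICCs.

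**Conclusion.** The gap is real and worth closing, but modest. Assignment is by week, and neither the primary comparison nor the mortality rule allows for it. The data list omits the one field needed to do so.

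If the week order is random, the Mann-Whitney reading of the primary analysis has a type I error of about 5% at ICC 0 to 0.02, 6% at 0.05 and 7% at 0.10, or about 9% at 0.10 if 200 men accrue in 52 weeks. Mortality at each look is about 6 to 8% with an uncorrected z test at ICC 0.05 to 0.10 and about 4 to 5% with Fisher's test, so week is secondary there. Under strict alternation with smooth drift there is no inflation.

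These sizes rest on assumed ICCs, Poisson weekly counts, 25% deaths, and tests that the plan does not name. The true effect may be negligible.

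**What to change.** 1. Add a coded week identifier, not a date, to REDCap before the master list is retired. A code respects the statement in Section 15 that the database holds no PHI.
2. State how the weeks were ordered, name the tests, and let the analysis follow the scheme actually used.
   - *Random order:* use a week-clustered rank test or a week-level re-randomisation test for the primary outcome. For mortality, including the 6- and 12-month looks, use a week-aware test that is valid with few weeks, such as week-level re-randomisation that follows the scheme and includes weeks with no patients.
   - *Alternating weeks:* keep the ordinary rank test as primary and report the week-clustered test as a sensitivity analysis, noting that it is conservative under smooth drift. Re-randomisation has no basis in that case, so any week-aware mortality comparison should be reported as approximate.
3. State in Section 6 that the 90% power assumes no correlation within weeks, and that 200 analysed men keep about 90% up to an ICC of roughly 0.05 to 0.09.

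**Cost.** One field, a few sentences and a little more analysis work; no extra patients. Standard errors widen by about 5% at ICC 0.05 (√1.096 = 1.047). Week-level re-randomisation for mortality costs about the same as Fisher's test and a few points of power against an uncorrected z test. For an assumed 25% v 10% deaths at ICC 0.05, power is 23% v 22% (Fisher) v 29% (z) at 26 weeks, and 47% v 46% v 52% at 52 weeks.

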9. DATA COLLECTION

Data collection procedures: to include lab evals, tests, specimen amounts and schedules, clinical assessments/schedule/follow up procedures, case report forms, data collection forms (with description of subject codes), study instruments, rating scales, interview guides.

RedCap Database to be created with the following data

Age (years)

Penetrating Trauma (0=no, 1=yes)

Penetrating Mechanism (1=stab, 2=gsw, 3=impalement, 9=other)

Blunt Mechanism (1=MVC, 2=Fall, 3=MCC, 4=ped vs auto, 5=assault, 9=other)

Scene transport (0=no, 1=yes)

Injury Severity Score (1-75)

Abbreviated Injury Score-Head (0-6)

Predominant site of hemorrhage (1=upper extremity, 2=lower extremity, 3=axilla, 4=groin, 5=head/neck, 6=chest, 7=abdomen, 8=pelvis, 9=other)

Tourniquet in Place (0=no, 1=yes)

Pre-LLUMC PRBC (# units)

Pre-LLUMC FFP (# units)

Pre-LLUMC PLT (# unitss

Pre-LLUMC Cryo (# units)

Pre-LLUMC Crystallloid (# liters)

Pre-LLUMC Cardiac Arrest? (0=no, 1=yes with ROSC, 2=yes without ROSC)

Arrival SBP (0 = in arrest)

Arrival HR (0 = in arrest)

Arrival Temperature (Celsius)

Arrival O2 saturation (0 = in arrest)

Arrival GCS (3-15)

Treatment Group (0 = Component Therapy, 1 = LTO+WB)

LLUMC ED WB (# units)

LLUMC ED PRBC (# units)

LLUMC ED FFP (# units)

LLUMC ED PLT (# unitss

LLUMC ED Cryo (# units)

LLUMC ED Crystallloid (# liters)

LLUMC ED Cardiac Arrest? (0=no, 1=yes with ROSC, 2=yes without ROSC)

LLUMC ED Thoracotomy (0=no, 1=yes)

LLUMC ED Laparotomy (0=no, 1=yes)

LLUMC ED Death? (0=no, 1=yes)

LLUMC ED ABG results

pH

Hgb

Lactate

LLUMC ED Hgb from CBC

LLUMC ED PLT count from CBC

LLUMC ED INR

LLUMC ED PTT

LLUMC ED Fibrinogen

LLUMC ED ROTEM results

EXTEM CT

EXTEM A10

If EXTEM A10 < 40mm, FIBTEM A10

EXTEM ML

Hemorrhage Control Environment (HCE) (0=none, patient died in ED, 1=none, patient direct to ICU, 2=OR, 3=IR, 4=OR and IR, 5=Hybrid OR)

LLUMC HCE WB (# units)

LLUMC HCE PRBC (# units)

LLUMC HCE FFP (# units)

LLUMC HCE PLT (# unitss

LLUMC HCE Cryo (# units)

LLUMC HCE Crystalloid (# liters)

LLUMC HCE Cardiac Arrest? (0=no, 1=yes with ROSC, 2=yes without ROSC)

LLUMC HCE Thoracotomy (0=no, 1=yes)

LLUMC HCE Laparotomy (0=no, 1=yes)

LLUMC HCE Pelvic Packing (0=no, 1=yes)

LLUMC HCE Neck Exploration (0=no, 1=yes)

LLUMC HCE Exploration for Axilla/Upper Extremity (0=no, 1=yes)

LLUMC HCE Exploration for Groin/Lower Extremity (0=no, 1=yes)

LLUMC HCE Death? (0=no, 1=yes)

LLUMC HCE ABG results #1 (first in HCE)

pH

Hgb

Lactate

LLUMC HCE ABG results #2 (last in HCE)

pH

Hgb

Lactate

LLUMC HCE ROTEM results #1 (first in HCE, if sent)

EXTEM CT

EXTEM A10

If EXTEM A10 < 40mm, FIBTEM A10

EXTEM ML

LLUMC HCE ROTEM results #2 (last in HCE, if sent)

EXTEM CT

EXTEM A10

If EXTEM A10 < 40mm, FIBTEM A10

EXTEM ML

LLUMC ICU/Floor Transfusion within first 24 hours (not including blood given prior to LLUMC, in LLUMC ED, and in LLUMC HCE)

LLUMC ICU WB (# units)

LLUMC ICU PRBC (# units)

LLUMC ICU FFP (# units)

LLUMC ICU PLT (# unitss

LLUMC ICU Cryo (# units)

LLUMC ICU Crystalloid (# liters)

LLUMC ICU ABG results

pH

Hgb

Lactate

LLUMC ICU Hgb from CBC

LLUMC ICU PLT count from CBC

LLUMC ICU INR

LLUMC ICU PTT

LLUMC ICU Fibrinogen

LLUMC ICU ROTEM results

EXTEM CT

EXTEM A10

If EXTEM A10 < 40mm, FIBTEM A10

EXTEM ML

Clinical Endpoints

Patient Dead on Arrival (0=no, 1=yes)

Patient Died within 6 hours of arrival (0=no, 1=yes)

Patient Died within 24 hours of arrival (0=no, 1=yes)

Patient Died Prior to Discharge (0=no, 1=yes)

Duration of Mechanical Ventilation (Days)

Duration of ICU Stay (Days)

Duration of Hospital Stay (Days)

Presence of ARDS?

Presence of TRALI?

Presence of DVT/PE?

SOFA Score on Day of ICU Discharge

Need for Dialysis During Hospitalization (0=no, 1=yes)

10. LABELING & STORAGE OF DATA & SPECIMENS

No data to be stored in hard copy form. Data will be entered into secure REDCAP database, with a master list correlating study ID number, MRN, and treatment arm to be kept on LLUMC secure server.

11. DATA ANALYSIS

Analysis to be performed by median/IQR with nonparametric comparison of medians for central tendency. P value of 0.05 indicates statistical significance. Patients with death on arrival will be excluded from data reporting as they are a different patient population. Intentional sub-analysis will be performed on patients who received less than 6 units PRBC or equivalent in the first 4 hours or 6 units and more PRBC in the first 4 hours (massive transfusion). Also, an intentional sub-analysis will be performed on the patients who were classified as dead on arrival. Separate sub-analyses will be performed on patients with Abbreviated Injury Score (Head) of 3 or greater indicating severe traumatic brain injury.

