8. STUDY DESIGN

a. Background or rationale for this study.

Whole blood transfusion was used in World War I, World War II, Korea and Vietnam. By the end of the Vietnam conflict, whole blood had been separated into components for ease of use and more focused transfusion. As a result, transfusion practices did not catch up with the available units. More recent investigations have revealed that patients have fewer deaths from hemorrhage when the ratios of FFP:RBC units and platelet:RBC units approaches 1:1. Furthermore, the success of “walking blood banks” with fresh whole blood transfusion in the 2nd Iraq war and the war in Afghanistan have prompted new interest in the civilian use of whole blood. While civilian centers cannot use walking blood banks as we do not have a pre-screened population from which to draw, low-titer type O positive whole blood (LTOWB) can be used. One LTOWB unit is equivalent to one unit of PRBC and one unit of FFP. While LTOWB has been studied, the inclusion criteria for past studies has been less inclusive than in this trial, specifically excluding patients with severe traumatic brain injuries even if they also had exsanguinating hemorrhage. Furthermore, at Loma Linda University Medical Center we will have the opportunity to randomize patients to receive whole blood as their first transfusion, thus maximizing the potential benefits. Finally, we have the opportunity to study the coagulopathy associated with these patients by using viscoelastic testing.

b. Objectives

1. Evaluate PRBC equivalents transfused in each group in the first 24 hours (Primary outcome)
2. Evaluate total transfusion in each group in the first 24 hours (Secondary Outcome) including breakdown by FFP equivalents, platelet units, and cryoprecipitate
3. Evaluate 6 hour, 24 hour, and hospital mortality (Secondary Outcome)
4. Evaluate ICU outcomes in each group:
 1. ICU length of stay

- 2. Ventilator days
- 3. SOFA score on day of ICU discharge
- 4. Presence of ARDS?
- 5. Presence of TRALI?
- 6. Presence of DVT/PE?
- 7. Necessity for Dialysis?
- 8. Necessity for Tracheostomy?
- 5. Evaluate viscoelastic testing parameters in both groups when sent on arrival in ICU
 - 1. Percentage of patients with EXTEM clotting time > 80 sec
 - 2. Percentage of patients with EXTEM amplitude at 10 min < 40mm and FIBTEM amplitude at 10 min \leq 10mm
 - 3. Percentage of patients with EXTEM amplitude at 10 min < 40mm and FIBTEM amplitude at 10 min > 10mm

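### The primary analysis uses neither the arrival variables already collected nor the randomisation week; one prespecified, week-respecting adjusted rank analysis would be modestly more precise and give a sounder standard error

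*Combined protocol and SAP*

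**What the plan says.** All references are to the combined protocol and SAP.

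- **Outcome.** Section 8b, objective 1: "Evaluate PRBC equivalents transfused in each group in the first 24 hours (Primary outcome".
- **Analysis.** Section 11: "Analysis to be performed by median/IQR with nonparametric comparison of medians for central tendency", followed by "P value of 0.05 indicates statistical significance". The rest of section 11 deals with dead-on-arrival patients and sub-analyses by transfusion volume and head injury. It names no covariate, stratum or week term.
- **Data available.** Section 9 lists, among others, "Arrival SBP (0 = in arrest", "Pre-LLUMC PRBC (# units", arrival heart rate (also coded 0 in arrest), arrival GCS and penetrating trauma.
- **Allocation.** Section 8c has the blood bank assign the arm by week from a calendar fixed in advance.
- **Sizing.** Section 6 takes from the earlier randomised trial that "median transfusion in the component therapy group was 6 PRBC in the first 24 hours and 4 PRBC equivalents in the whole blood group". It adds: "The standard deviation (estimated from the interquartile range) was approximately 4". It then claims "expected power of 90% to detect a similar 2 unit difference in transfusion volume" with 190 patients, and projects 200.

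**The concern.** Eligibility is broad (adult men with Level A activation receiving emergency transfusion, severe brain injury included), so transfusion volume should vary widely with severity on arrival. An unadjusted comparison leaves all of that variation in the error term. The arrival variables are recorded at or before arrival, so the study blood cannot plausibly have altered them, and they are already in the database.

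Patients arriving in the same week share an arm. If they also resemble one another, a test that treats all patients as independent understates the standard error. If one arm happens to receive the more severe weeks, the plan has no prespecified adjusted result to set beside the unadjusted one, and an adjustment chosen afterwards would be open to challenge.

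**Working it through.** **Inputs from the documents.** Difference 2 units, SD 4, alpha 0.05, power 90%, required N 190, planned N 200 (section 6); study dates 07/01/2021 to 06/30/2023 (section 4). **Assumed:** two-sided test, 1:1 allocation, share of variance explained by the covariates (R²) of 0.10-0.30, within-week ICC of 0.01-0.10. The documents give none of these.

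**1. The plan's own figure.** n per arm = 2(1.960 + 1.282)² × 4² / 2² = 84.1, so 85 per arm and 170 in total (172 by the exact t-test; 180 for a Wilcoxon test with efficiency 0.955). The stated 190 is not reproduced. It would follow from 85/0.90 = 94.4, so 95 per arm, but no 10% allowance is stated. Since 190 exceeds 170-180, this is not under-sizing.

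**2. Unadjusted power at N=200.** SE = 4 × √(2/100) = 0.566. Then 2/0.566 − 1.96 = 1.576, which gives power 94.2% (94.0% by the t-test). For Wilcoxon, 200 × 0.955 = 191 effective patients, giving about 93%.

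**3. Adjusted power.** The residual SD is 4√(1 − R²) and the effective N is 200/(1 − R²). Power by the t-test:

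| R² (assumed) | Residual SD | Effective N | Power, 2 units | Power, 1.5 units |
|---|---|---|---|---|
| 0 | 4.00 | 200 | 94.0% | 75.1% |
| 0.10 | 3.79 | 222 | 96.0% | 79.4% |
| 0.20 | 3.58 | 250 | 97.6% | 83.9% |
| 0.30 | 3.35 | 286 | 98.8% | 88.4% |

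The 1.5-unit column is illustrative; that effect is not in the documents.

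**4. Check on the proposed method.** Step 3 is a t-test calculation, so rank ANCOVA was also simulated (2,000 runs, N=200, one covariate, no clustering). With normal data, Wilcoxon had about 93% power and rank ANCOVA about 96% at R² 0.20 and 98% at R² 0.30. With skewed counts around medians of 6 and 4, Wilcoxon already had about 99%, so there was less to gain.

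**5. Week of allocation.** The study lasts about 104 weeks, so m = 200/104 = 1.92 patients per week. With Poisson-varying weekly numbers the design effect is 1 + m × ICC. The true type I error of a test that ignores weeks is 2Φ(−1.96/√design effect).

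| ICC (assumed) | Design effect | Unadjusted power, 2 units | Type I error if weeks are ignored |
|---|---|---|---|
| 0.01 | 1.02 | 93.8% | 5.2% |
| 0.05 | 1.10 | 92.2% | 6.1% |
| 0.10 | 1.19 | 89.9% | 7.3% |

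**6. Both together.** Take R² = 0.10 and a residual ICC still at 0.10. The variance factor is 0.90 × 1.192 = 1.073, and SE = 4 × √(0.02 × 1.073) = 0.586. Then 2/0.586 − 1.96 = 1.453, giving power of about 93%. A small gain from covariates therefore about pays for a week-respecting standard error.

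**The case against.** An unadjusted rank comparison is a legitimate primary analysis in a randomised trial, and nothing in section 11 contradicts another section on this point. At the planned effect the design already exceeds its 90% target, so adjustment adds only about 2 to 5 points. No R² is documented, and coding arrest as 0 for SBP and HR may weaken the covariates: patients in arrest may die early and receive few units, so the relation to volume need not be monotone. All of this stands. It limits the size of the point and shapes the fix.

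Three stronger readings are tempting, and the documents do not support them.

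- **That the plan delivers only about 78% power.** This takes the analysis to be a literal median test: 190 × 0.637 = 121 effective patients. It needs normal data and N=190; at the planned 200 the figure is about 80%, and with the skewed counts of step 4 about 92%. The section 11 wording is commonly shorthand for the Wilcoxon test. At most, the test should be named.
- **That a run of severe weeks would bias the result.** If weeks are randomised, such a run is chance imbalance. It widens the uncertainty and does not shift the expected estimate.
- **That the unadjusted analysis wastes much power.** A gain of 4 to 13 points arises only at a 1.5-unit effect, which the protocol does not plan for. A smaller effect than 2 units is plausible, because section 8f says the earlier trial excluded significant brain injury and this trial does not. Its size is unknown.

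**Conclusion.** The point holds in a limited form. The primary analysis ignores both the prognostic arrival data and the unit of allocation. At 2 units, SD 4 and N=200, adjustment lifts power from about 93-94% to about 96-99%, given an assumed R² of 0.10-0.30. The direction holds for any R² above 0.

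The week matters for the standard error: a design effect of about 1.02-1.19 for an assumed ICC of 0.01-0.10 takes a nominal 5% test to roughly 5-7%. Covariate adjustment deals with only part of this, so the week has to be handled in the inference as well. This is a worthwhile improvement at little cost; the trial is not invalid or under-sized on this account.

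**What to change.** In section 11, prespecify a single primary analysis of 24-hour PRBC equivalents:

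- rank-based ANCOVA on assigned arm;
- adjusted for arrival SBP, arrival HR, arrival GCS, penetrating mechanism and pre-arrival PRBC units;
- a separate indicator for arrest on arrival, so that the 0 codes for SBP and HR are not read as measurements;
- inference either clustered on randomisation week or by permutation of weeks under the actual calendar scheme, with one of the two chosen in advance;
- no adjustment for laboratory results or transfusions recorded after study blood could have been given.

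Keep the unadjusted Wilcoxon rank-sum test, named as such, and the medians with IQRs by arm as supporting results. The effect is then still reported in units, which a proportional-odds model would replace with an odds ratio.

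The cost is slightly more programming, a short rule for missing arrival values, and a slightly wider interval if weeks are correlated. No new data items or patients are needed.
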